22.3 Appendix C-Augmented Numerical Rating Scale

THE STEADMAN CLINIC
AND
STEADMAN PHILIPPON RESEARCH INSTITUTE

APPROVED

Clinical Trial #2019-16: Pain Questionnaire

Greetings from The Steadman Clinic!

This short pain questionnaire is part of the clinical trial that you are participating in at The Steadman Clinic.

We thank you very much for your time!

If you have missed an item, it will appear in **RED**. At the end of the , there is a submit button. Once you click the submit button, a new page with a "Thank You for Your Response" message will appear.

There is no need to print this form.

On a scale of 0 to 10 please describe your current level of knee pain:

Today: 0 - No Pain 1 2 3 4 5 6 7 8 9 10 - Severe Pain

At its worst: 0 - No Pain 1 2 3 4 5 6 7 8 9 10 - Severe Pain

Following activity: 0 - No Pain 1 2 3 4 5 6 7 8 9 10 - Severe Pain

Please select the one response that best reflects your knee pain:

- None or you ignore it Moderate pain, tolerable but concessions to pain are made.
 Slight, occasional, no compromise in activity Marked pain, serious limitations of activity
 Mild, no effect on average activities Totally disabled, crippled, pain in bed, bedridden

After 6 to 9 blocks (about 1 mile), please describe how you would walk: *

- No limp Slight limp Moderate limp Severe limp

How much trouble do you have with...

Stiffness in your knee? * NONE MILD MODERATE SEVERE EXTREME

Decreased motion of your knee? * NONE MILD MODERATE SEVERE EXTREME

How would you rate your current level of function? *

- Normal Nearly Normal Abnormal Severely Abnormal

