9.1 Enrollment Criteria

9.1.1 Inclusion Criteria

Subjects will be included if all of the following criteria are met:

1. Are male or female, ages 40-80;
2. Are willing to comply with all study related procedures and assessments;
3. Are ambulatory as defined by ability to complete functional performance testing;
4. Radiographic evidence of Kellgren-Lawrence grade II-IV osteoarthritis in one or both knees;
5. Scores 4-10 on the Numerical Rating Scale (NRS) for pain;
6. Stable dose of screening/baseline medications for at least 2 months prior to the anticipated date of study drug dosing.

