11.5 Patient Reported Outcomes (PROs): (Visits 1, 2, 4, 5, 6)

All PROs may be completed either on paper documents or by online questionnaire administration conducted via formsite (Vroman Systems, Inc.). Patients may complete questionnaires on a variety of electronic devices (personal computer, mobile phone, tablet).

PRO data to be collected include:

Augmented Numerical Rating Scale (NRS) (visit 2): At baseline then once every 3 days during FIRST 6 weeks of study medication treatment then once a week for an ADDITIONAL 6 weeks.

IKDC, Lysholm, TEGNER, WOMAC and SF-12 (visit 2, visits 4, 5, and 6 and remote assessments at 3- and 18-months post completion of medication).

The Numerical Rating Scale is a simple 0-10 self-reported severity of pain scale, (zero being no pain and 10 being the worst pain imaginable). This tool has been validated to provide excellent test-retest reliability in assessing knee pain associated with OA³¹. The Steadman Philippon Research Institute has added several stand-alone questions that are administered with the questionnaire. Only the validated portion, the simple NRS will be used to screen patients. In follow-up, each question will be analyzed individually. There is no composite score. A sample can be found in **Appendix C, Section 22.3** of this document.

The Lysholm knee scale is a condition-specific outcome measure that was originally designed to assess ligament injuries of the knee. It has been tested to provide excellent construct validity and overall acceptable psychometric performance for outcomes assessment of various chondral disorders of the knee. It is recommended that this tool be administered with additional psychometric measurements^{32,33}.

The TEGNER Activity Scale is a numerical scale ranging from 0 to 10. Each value indicates the ability to perform specific activities. An activity level of 10 corresponds to participation in the most physically demanding activities while a zero is assigned if a person is on sick leave or receiving a disability pension because of knee problems. It is simple to use, and it has been demonstrated to provide acceptable psychometric performances as outcome measures for patients with a meniscal injury of the knee. Like the Lysholm, it is recommended that it be used in conjunction with other psychometric tools such as the SF 12³².

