15.5.2.3 Pain and PRO Assessment

The hypothesis in this study is that FIS will induce a systemic anti-inflammatory and senolytic effect, thereby reducing pain and improving self-reported function and quality of life compared to the placebo group. Early subjective assessment (every 3 days for 6 weeks following the first dose of study medication and once weekly for the following 6 weeks) will be limited to a short augmented numerical rating scale questionnaire. Linear mixed-effect random-intercepts modeling will be used to characterize the trend in self-reported pain over 3 months, and to test whether treatment group is a significant predictor of pain reduction.

The IKDC, WOMAC, Tegner activity scale and Lysholm PRO measures will be administered at 2 weeks after the last dose of study medication and 6, 12, and 18 months following initiation of medication. For each time point, ANCOVA will be used with the subject's baseline PROM value used as a covariate. Among the 4 postoperative time-points for assessing these validated PROMs, the Holm-Bonferroni method will be used to control the family-wise type-1 error rate to 0.05 within each PROM scale tested. No multiplicity adjustments will be made across different PROMs, which are commonly highly intercorrelated.

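### The Appendix C pain form does not use the top anchor described in section 11.5, does not name the Study Knee, and has no item designated as the NRS for entry criterion 5 or the 12-week pain test

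*Combined protocol and SAP*

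**What the plan says.** Section 9.1.1, criterion 5, requires "Scores 4-10 on the Numerical Rating Scale (NRS) for pain". It names no item, recall period or knee. Criterion 4 accepts "Radiographic evidence of Kellgren-Lawrence grade II-IV osteoarthritis in one or both knees".

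Section 11.5 describes one simple 0-10 scale, "zero being no pain and 10 being the worst pain imaginable", cites evidence of its reliability in knee OA, and refers to Appendix C (section 22.3) for a sample. It also discloses that the institute "has added several stand-alone questions that are administered with the questionnaire". For use of the form it gives two rules: "Only the validated portion, the simple NRS will be used to screen patients", and "In follow-up, each question will be analyzed individually", with no composite.

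The form in Appendix C opens by asking for the present level of pain in the knee. Three 0-10 items follow: *Today*, *At its worst* and *Following activity*. All three have the same end labels, as in "Today: 0 - No Pain 1 2 3 4 5 6 7 8 9 10 - Severe Pain". Five categorical questions come after them. No side is asked for, and the Study Knee is not mentioned.

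Section 15.5.2.3 uses this form every third day for six weeks and then weekly for six more. A random-intercepts mixed model is to "characterize the trend in self-reported pain over 3 months" and to test whether treatment group predicts the reduction. The item is not named. Holm-Bonferroni is planned across time points within IKDC, WOMAC, Tegner and Lysholm. No rule is given for the NRS items.

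**The concern.** Patients complete the form, not the description in section 11.5. If the form is used as printed, three things follow.

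- **Anchor.** The entry cut-off of 4 is applied to a scale whose top label differs from the one that section 11.5 calls validated. The responses cannot be converted afterwards.
- **Knee.** A patient with OA in both knees can answer for either knee, or for whichever hurts more that day. Objectives 2 and 4 in the synopsis refer to the Study Knee. Pain in such a patient may therefore belong to a different joint from the one imaged, and section 8.2.2 plans to look at correlation among endpoints.
- **Item.** Screening staff and analysts must each decide which of three scores is the NRS. For the 12-week test there is neither a lead item nor a multiplicity rule.

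The form supplies the only scheduled pain measure while subjects are being dosed, because the other questionnaires first recur at Visit 4.

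**Working it through.** **1. The plan's own figure.** No sample size or power is stated for the NRS. The only such figure is for T1rho in section 15.6: SMD 0.73, two-sided 0.05, 80% power, 30 per group. It reproduces: 2 × (1.960 + 0.842)² / 0.73² = 29.5, rounded up to 30. Nothing in this point changes it.

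**2. The sections side by side.**

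| Feature | Sections 9.1.1, 11.5, 15.5.2.3 | Appendix C |
|---|---|---|
| Top anchor | worst imaginable pain | severe pain, on all three items |
| Number of 0-10 pain items | one simple NRS, plus added questions | three |
| Item used for criterion 5 | the simple NRS, not identified | none marked |
| Item used in the 12-week model | not named | none marked |
| Recall period for *At its worst* | not given | not given; lead-in asks about the present |
| Knee | criterion 5 names none; one or both knees eligible | no side, no Study Knee |

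The anchor row is a contradiction. The item, recall and knee rows are gaps that no other section fills. The added questions are not a contradiction, because section 11.5 discloses them.

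**3. How often the form is used.** Six weeks at one form per 3 days is 42 / 3 = 14. Six weekly forms bring it to 20, or 21 if day 1 is counted separately. With three 0-10 items each, that is 60 to 63 pain scores per subject. Visit 4 falls at day 32 + 14 = 46, with a window of days 36 to 56. The other questionnaires therefore miss the dosing period (days 1 to 32) but do fall within the 84-day diary.

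**4. No lead item: false positives.** Suppose each of the three items is tested at 0.05 without adjustment. If they are independent, the chance of at least one false positive is 1 − 0.95³ = 14.3%. The items are surely correlated, but the documents give no correlation. Simulating three equally correlated normal test statistics gives 12.6% at 0.5, 10.9% at 0.7 and 8.4% at 0.9.

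**5. No designated item: eligibility.** This is an illustration only, and none of its inputs come from the documents. Assume that *Today* has mean 3 to 5 and SD 2 in screened patients, and that *At its worst* is on average about 1 to 3 points higher. Then about 11% to 47% of those screened fall below 4 on *Today* but reach 4 on *At its worst*. The range is too wide to be an estimate. It shows only that the choice of item is not neutral, and the problem disappears if *Today* is always used.

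**6. Knee.** The documents give neither the share of bilateral patients nor the share of those with pain in both knees, so no size can be computed.

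**The case against.** The strongest defence is that section 11.5 already handles the form. It discloses the extra questions, limits screening to the simple NRS, says every question is analysed individually and rules out a composite. Under a lead-in about present pain, *Today* is the obvious simple NRS. This stands. A reader might infer that no usable pain score exists, or that the plan lets the analyst report only the most favourable item. The documents support neither reading. What remains is that the score is not designated and that the test has no lead item.

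A reader might also infer that the milder top label lets in patients below the intended threshold and pushes severe patients to the ceiling. That needs an assumption about how patients map one label to the other, which the documents do not supply. Criterion 5 runs up to 10, so a ceiling score excludes nobody. Both arms use the same form, so the anchor does not by itself bias the comparison between them.

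On the knee, a reader might infer that every bilateral patient is affected, or that a recently treated other knee is generally free to distort the score. Some patients with bilateral radiographic OA will have only one painful knee. Exclusion 5d on steroid injection is not limited to the Study Knee, 5b requires a replaced contralateral knee to be asymptomatic, and 5c bars planned arthroscopy on either knee. Among injections, only biologic or hyaluronic acid treatment of the other knee falls outside the exclusions. The drug is oral with a hypothesised systemic effect, and the walking tests are not knee-specific. These points narrow the mismatch mainly to pain against MRI.

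Finally, the primary endpoint is adverse events, section 8.2.2 does not list the NRS among the questionnaires, and WOMAC also covers pain at Visit 4. This limits the impact. Section 15.5.2.3 nevertheless plans a treatment test on the diary, and criterion 5 depends on the scale.

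**Conclusion.** The point holds, with minor severity. Three facts can be read directly from the text: the top anchor differs between section 11.5 and Appendix C, no item is designated for criterion 5 or the 12-week model, and the form does not identify the Study Knee although bilateral OA is eligible. As a result, entry scores are not on the scale that section 11.5 relies on, and in bilateral patients entry and diary pain may describe a different joint from the MRI. Neither effect can be sized from the documents. Whether the anchor wording changes the measurement properties also cannot be judged without the cited reliability study. The one calculable consequence, a false-positive chance of roughly 8% to 14% in place of 5%, assumes three unadjusted tests and correlations between 0.9 and 0.

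A reader might go further and conclude that the Study Knee must be defined as the more painful knee. The finding does not need that. It would be a new eligibility rule, whereas recording which knee is under study is enough.

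**What to change.** - **Appendix C:** use the top anchor stated in section 11.5 on the 0-10 items. Rewording section 11.5 to match the form would also remove the contradiction, but would give up the claimed match to the validated scale.
- **Appendix C:** word the knee questions to the Study Knee, with the side pre-filled, and record that side before randomization.
- **Appendix C:** give *At its worst* a recall period equal to the interval since the last form, which is 3 days and then one week.
- **Sections 9.1.1 (criterion 5) and 15.5.2.3:** designate one item as the NRS for both entry and the 12-week model, and call the other two supportive. *Today* is the natural choice. With one lead item, no multiplicity adjustment is needed for this test.

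The cost is a form and protocol amendment with IRB approval under sections 16.2 and 18.7, plus a flag on data already collected with the present wording. Sample size, visits and the analysis model do not change.

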22.4 Appendix D: Potential Drug Interactions with Fisetin

Fisetin has been demonstrated to have inhibitory activity of cytochrome P450

Fisetin has been demonstrated to have inhibitory (competitive mainly) activity of cytochrome P450 isozymes especially CYP2C9 and CYP3A4. CYP2C9 is an important cytochrome P450 isozyme with a major role in the oxidation of both xenobiotic and endogenous compounds. CYP2C9 makes up about 18% of the cytochrome P450 protein in liver microsomes (data only for antifungal). Some 100 therapeutic drugs are metabolized by CYP2C9, including drugs with a narrow therapeutic index such as warfarin and phenytoin and other routinely prescribed drugs such as acenocoumarol, tolbutamide, losartan, glipizide, and some nonsteroidal anti-inflammatory drugs. CYP3A4 is a critical hepatic “first-pass” metabolism enzyme for a litany of drugs including Fisetin which is estimated to be responsible for approximately 40-50% of Fisetin’s bioavailability loss upon oral administration. As a competitive inhibitor of CYP3A4, Fisetin can thus significantly modulate the serum concentrations of other co-administered drugs that have narrow therapeutic ranges, potentially leading to adverse effects. Several classes of drugs are metabolized by cytochrome P450 isozymes. These again include anti-coagulants (i.e. warfarin or Acenocoumarol), diabetes drugs or gluco-regulatory drugs (i.e. Tolbutamide or Glucotrol), anti-seizure drugs (i.e. Phenytoin or Dilantin). To accommodate for this, we have constructed an exclusion criteria to mitigate these effects and provide a list of drugs known to interact with crucial CYPs that must be withheld for 2 days prior to Fisetin dosing and during Fisetin administration.
